AUC _{0-6h}	Area Under the Curve from time zero to 6h
AUC _{0-last}	Area Under the Curve from time zero to last measurable plasma concentration
AUC _{0-inf}	Area Under the Curve from time zero to infinity
BLQ	Below the Limit of Quantification
BMI	Body Mass Index
C _{last}	Last measurable plasma concentration
C _{max}	Maximum observed plasma concentration
CI	Confidence Interval
CL	Total body clearance
CysC	Cystatin C
CRF	Case Report Form
CV	Coefficient of Variation
DBP	Diastolic Blood Pressure
ECG	ElectroCardioGram
FDA	Food and Drug Administration – U.S. authority
FIH	First-In-Human
FXI	Factor XI
FXII	Factor XII
GGT	Gamma Glutamyl Transferase
hsCRP	high sensitivity C-Reactive Protein
HBsAg	Hepatitis B surface Antigen
HCV	Hepatitis C Virus

ABBREVIATION	DEFINITION
HIV	Human Immunodeficiency Virus
i.e.	id est
ICF	Informed Consent Form
ICH	International Conference on Harmonisation
IMP	Investigational Medicinal Product (synonymous with “study drug”)
Ir-CPI	Ixodes ricinus-Contact Phase Inhibitor
IS	Included Set
λ_z	Terminal elimination rate constant
KIM	Kidney Injury Molecule
LDH	Lactate Dehydrogenase
LLN	Lower Limit of Normal range
LLOQ	Lower Limit of quantification
MedDRA	Medical Dictionary for Regulatory Activities
ND	Not Determined
NGAL	Neutrophil Gelatinase-Associated Lipocalin
NOAEL	No Observed Adverse Effect Level
PCSA	Potentially Clinically Significant Abnormalities
PD	PharmacoDynamics
PDS	PharmacoDynamics Set
PK	PharmacoKinetics
PKS	PharmacoKinetic Set
PT	Preferred Term
QRS	QRS interval duration
QT	Time interval for ventricular depolarisation and repolarisation
QTc	Corrected QT interval
QTcB	QT interval corrected using Bazett’s formula
QTcF	QT interval corrected using Fridericia’s formula
RS	Randomised Set
SAD	Single Ascending Dose
SAE	Serious Adverse Event
SAP	Statistical Analysis Plan
SAS [®]	Statistical Analysis System [®]
SBP	Systolic Blood Pressure
SD	Standard Deviation

ABBREVIATION	DEFINITION
SEM	Standard Error of the Mean
SOC	System Organ Class
SpO ₂	Peripheral Capillary Oxygen Saturation
SRC	Safety Review Committee
SS	Safety Set
SVT	SupraVentricular Tachycardia
t _{1/2}	Terminal elimination half-life
t _{max}	time to reach maximum observed plasma concentration
TEAE	Treatment-Emergent Adverse Event
TNF	Tumor Necrosis Factor
ULN	Upper Limit of Normal range
V _d	Volume of distribution
VT	Ventricular Tachycardia
WHO	World Health Organisation

1. Introduction

The Statistical Analysis Plan (SAP) details the statistical methodology to be used in analysing study data and outlines the statistical programming specifications, tables, figures and listings. It describes the pharmacokinetics, pharmacodynamics, safety and tolerability variables and populations, anticipated data transformations and manipulations, and other details of the analyses not provided in the study protocol.

The analyses described are based upon the final clinical study protocol V4.0 dated 06 December 2019 and minutes of Safety Review Committee (SRC) meetings, and are prepared in accordance with the International Conference on Harmonisation (ICH) E9 Step 4 version dated 05 February 1998 [1].

The statistical analyses will be performed by the Biostatistics unit of BIOTRIAL BIOMETRICS in agreement with the Sponsor.

The SAP will be validated and signed before the study database is locked.

2. Study objectives

2.1. Primary objectives

The primary objectives are:

- Part 1: To assess the safety and tolerability of Ir-CPI following a single ascending 6-hour intravenous infusion in healthy male participants.
- Part 2: To assess the safety and tolerability of Ir-CPI following a combination of rapid (30 minutes) and slow (5.5 hours) intravenous infusion over a total of 6 hours in healthy male participants (see Note at the end of this section).

2.2. Secondary objectives

Secondary objectives are:

- Part 1: To assess the pharmacokinetics (PK) of Ir-CPI following single ascending 6-hour intravenous infusion in healthy male participants.
- Part 2: To assess the PK of Ir-CPI following a combination of rapid (30 minutes) and slow (5.5 hours) intravenous infusion over a total of 6 hours in healthy male participants (see Note at the end of this section).
- Investigate the preliminary pharmacodynamics (PD) of Ir-CPI in healthy male participants using a validated method according to the Food and Drug Administration (FDA) guidelines 2018 for activated Partial Thromboplastin Time (aPTT). Inhibition of Factor XI (FXI) and Factor XII (FXII) procoagulant activities will also be assessed to support the aPTT dynamics.

2.3. Exploratory objectives

Exploratory objectives are:

- Investigate the potential of Ir-CPI to induce the formation of anti-drug antibodies (ADA), including their capability to neutralize drug activity.
- Investigate the effect of Ir-CPI on markers related to the coagulation system.
- Investigate the effect of Ir-CPI on biomarkers of renal injury.
- Investigate the effect of Ir-CPI on inflammatory markers.

- Assess the PK of Ir-CPI in urine.
- PK PD relationship (graphical analyses).

Note: Only the Part 1 was performed with 4 cohorts (A, B, C and D) (instead of Part 1 with 5 cohorts and Part 2 with 3 cohorts) and with the following doses discussed during SRC meetings:

- Cohort A: Ir-CPI 1.5 mg/kg;
- Cohort B: Ir-CPI 3 mg/kg;
- Cohort C: Ir-CPI 6 mg/kg;
- Cohort D: Ir-CPI 9 mg/kg.

Consequently, in all the following descriptions, only the Part 1 will be detailed in this SAP.

3. Study methodology

3.1. Study design

This study is a First-In-Human (FIH) Phase 1, double-blind, placebo controlled, single dose escalation study of Ir-CPI in healthy male participants.

The study will consist of:

- Part 1: an Ir-CPI or matching placebo single ascending dose administration in healthy male participants using a continuous 6-hour intravenous infusion.

The flowchart of this study is detailed in section 16.1.

In all the following descriptions, the term *postdose* is defined as « after start of infusion ».

The terms *panel* and *cohort* can be used interchangeably.

3.2. Randomisation

For this double blind, placebo-controlled, ascending dose trial of single dose infusions of Ir-CPI/Placebo, the participants will be randomised taking into account the specific requirements for the sentinel groups.

Four (4) panels (A to D), each consisting of eight (8) healthy male participants will be randomised to receive either Ir-CPI or matching placebo: first, 2 sentinel participants (1:1 active / placebo) then for the rest of the group, a 5:1 ratio (active / placebo). The four (4) panels will be administered Ir-CPI/Placebo in a sequential group design.

3.3. Treatment(s) received

An Ir-CPI or matching placebo single ascending dose will be administered to the participants using a continuous 6-hour intravenous infusion.

Each of the four (4) panels will receive:

- Cohort A: Ir-CPI 1.5 mg/kg;
- Cohort B: Ir-CPI 3 mg/kg;
- Cohort C: Ir-CPI 6 mg/kg;
- Cohort D: Ir-CPI 9 mg/kg.

3.4. Visits

For cohorts from A to D, the study will include the following visits (see section 16.1.1):

	Cohorts A, B and C	Cohort D
Screening	from Day-28 to Day -2 (Visit V1)	
Randomisation	Day 1 (pre-dose, Visit V3)	
Treatment period	from Day -1 (Visit V2) to Day 5 (Visit V7)	from Day -1 (Visit V2) to Day 7 (Visit V8)
Discharge visit	Day 10 (\pm 2 days) (Visit V8)	Day 10 (\pm 2 days) (Visit V9)
Extra ambulatory visits for ADA analysis	Day 30 (\pm 3 days) (1 month, Visit V9) Day 90 (\pm 7 days) (3 months, Visit V10) Day 180 (\pm 7 days) (6 months, Visit V11)	Day 30 (\pm 3 days) (1 month, Visit V10) Day 90 (\pm 7 days) (3 months, Visit V11) Day 180 (\pm 7 days) (6 months, Visit V12)

All participants will receive a single intravenous dose of Ir-CPI/Placebo at Day 1, given as a 6-hour infusion.

4. Sample Size

The number of participants is not based on statistical power considerations. A sample size of 8 participants per panel (i.e., 6 active and 2 placebo) was chosen based on the design of similar SAD studies and is considered adequate to provide an initial assessment of the safety and tolerability profile of Ir-CPI.

5. Changes to the planned analysis from protocol

The following changes are added compared to the planned analysis detailed in the study protocol:

- Addition of the Screened set (defined as all of the subjects having signed an informed consent form) (see section 7.1).
- Orthostatic hypotension and abnormal HR will not be derived because there are not standing vital signs measured during the study.
- Only the Part 1 was performed with 4 cohorts (A, B, C and D) (instead of Part 1 with 5 cohorts and Part 2 with 3 cohorts) and with the following dose modifications discussed during SRC meetings (see minutes of these meetings):
 - Cohort A: Ir-CPI 1.5 mg/kg;
 - Cohort B: Ir-CPI 3 mg/kg;
 - Cohort C: Ir-CPI 6 mg/kg;
 - Cohort D: Ir-CPI 9 mg/kg.
- In exploratory objectives, the investigation of the ADA capability to neutralize drug activity was not performed, and the assessment of the PK of Ir-CPI in urine was also not done.
- Addition of statistical analysis of AUC_{0-96h} and AUC_{0-last} (see section 9.2.2).

6. Statistical considerations

6.1. Software environment

Statistical analyses (demography, pharmacodynamics, safety and tolerability data) will be performed using SAS[®] software version 9.4 (SAS institute Inc. Cary NC USA).

PK parameters will be calculated using Phoenix[®] WinNonlin[®] version 8.1 (Certara USA, Inc., Princeton, NJ) and will be analysed using SAS[®] version 9.4 (SAS Institute Inc., Cary, NC, USA).

6.2. Descriptive statistics and data listings

Descriptive statistics will be supplied according to the nature of the criteria:

- Quantitative variable: sample size, arithmetic mean, standard deviation (SD), standard error of the mean (SEM), minimum, median and maximum, and [quartiles if necessary with geometric mean, arithmetic and geometric coefficients of variation (CV), and quartiles for PK parameters].
- Qualitative variable: sample size, absolute and relative frequencies per class. Percentages will be provided with one decimal place.

If the sample size of one treatment group is less than or equal to 2, only the number of observed values, the minimum and the maximum will be presented for quantitative variables and the percentage of subjects will not be presented for qualitative variables.

Unless specified otherwise, the calculation of percentages will be based on the number of observed values. Therefore, counts of missing values will be included in the denominator and displayed as a separate category if any.

Data will be organised by treatment group:

- Pooled Placebo;
- Ir-CPI 1.5 mg/kg;
- Ir-CPI 3 mg/kg;
- Ir-CPI 6 mg/kg;
- Ir-CPI 9 mg/kg.

All demographic, pharmacokinetics, pharmacodynamics, safety and tolerability listings will be sorted by treatment group, subject and measurement time if applicable.

All listings containing an evaluation date will display the study day defined as the day relative to the administration of study drug:

- Study day 1 will be defined as the day of the study product administration date;
- Study day -1 will be defined as the day prior to the study product administration date;
- There will be no study day 0.

6.3. Handling of missing and retest values

No management of missing values or values below/above a limit of detection/quantification will be performed, except for pharmacokinetic values (see section 0).

For all parameters and for subjects with retest values, the last reliable value will be used for the measurement time before the study drug administration (provided it was measured before

the study drug administration) and the first reliable value will be used for the measurement time after the study drug administration.

6.4. Handling of incomplete dates

No management of incomplete dates will be performed. The incomplete dates will be labelled as such in the listings.

If the start date of a medication or an adverse event is missing or incomplete and the end date is missing, on or after the study drug administration, it will be considered as concomitant/treatment emergent.

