All AEs judged by either the reporting Investigator or the Sponsor as having a reasonable causal relationship to a medicinal product qualify as an ADR.

All AEs for which the judgement of relationship to study medication is “possible” or higher will be considered ADRs.

• Treatment-Emergent Adverse Events

A treatment-emergent AE is an AE that occurs after IMP dosing or that was present prior to dosing but becomes exacerbated between dosing during a treatment period and the end of the study.

- **Abuse, Misuse, Medication Error and Overdose**

Abuse is defined as persistent or sporadic, intentional excessive use of IMP which is accompanied by harmful physical or psychological effects.

Misuse is defined as situations where an IMP is intentionally and inappropriately used not in accordance with the terms of the study protocol.

Medication error is defined as an unintended failure in the IMP administration process that leads to, or has the potential to lead to, harm to the participant.

Overdose is defined as intake of a quantity of an IMP given per administration or cumulatively which is above the maximum dose recommended in the study protocol.

Serious Adverse Events or Serious Adverse Drug Reactions

- **General definitions**

A Serious Adverse Event (SAE) is any untoward medical occurrence that at any dose:

- results in death,
- is life threatening,
- requires inpatient hospitalisation or prolongation of existing hospitalisation*,
- results in persistent or significant disability/incapacity,
- is a congenital anomaly/birth defect, or
- is an important medical event that requires intervention to prevent one of the above.

* *“Inpatient hospitalisation” is defined as 24hours in the hospital or an overnight stay.*

Additionally, a Serious Adverse Drug Reaction (SADR) is a SAE that occurs after IMP administration and is considered to have any potential causal relationship with the IMP according to the Investigator or the Sponsor.

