8.4. Previous and concomitant medications

Information on previous and concomitant medications will be coded according to the WHO drug Dictionary version of March 2019.

A previous medication will be defined as a relevant treatment received by the participant within 2 weeks before the study product administration. A concomitant medication will be defined as a medication the participant takes during the study and until the last extra ambulatory V11 visit only if related to a reported AE, other than the study drugs, including any prescription or over-the counter drug (including vitamins, herbal and mineral supplements). If the date value does not allow allocation of a medication to the previous or concomitant category (missing or incomplete start or end date), this medication will be considered concomitant.

A table with the number and percentage of subjects having taken at least one previous medication and a table with the number and percentage of subjects having taken at least one concomitant medication will be generated by treatment group and overall (overall and by medication class [2nd level of Anatomical Therapeutic Chemical (ATC)] and medication drug name). Previous and concomitant medications will be listed separately.

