13.1. Adverse events

Adverse events, including pre-treatment events, will be recorded from the time of consent through the end of the study.

Adverse events will be coded according to MedDRA Version 22.0.

A treatment-emergent adverse event (TEAE) is an adverse event that occurs after IMP dosing or that was present prior to dosing but was exacerbated between dosing during a treatment period and the end of the study.

Adverse events (including AESIs) will be summarised in tables as follows [overall and by System Organ Class (SOC) and Preferred Term (PT)]:

- Number and percentage of subjects with at least one adverse event and number of occurrences of an adverse event by treatment group and overall,
- Number and percentage of subjects with at least one TEAE and number of occurrences of a TEAE by treatment group and overall,
- By intensity, with the number and percentage of subjects with at least one TEAE and number of occurrences of a TEAE by treatment group and overall,
- By causality, with the number and percentage of subjects with at least one TEAE and number of occurrences of a TEAE by treatment group and overall.

If there are only a few adverse events (≤ 10), only a listing will be generated.

All adverse events reported in the Case Report Form (CRF) will be listed with the SOC, the PT and the Investigator's verbatim. All TEAEs will also be listed with the SOC and the PT. An additional listing will be provided for AEs leading to death and other serious and significant AEs (SAEs or AEs leading to study withdrawal).

Note: In case of a change of intensity or causality for an event during the treatment period, the intensity will be the highest recorded intensity and the causality will be the highest likelihood recorded.

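### SAP 6.4 makes an adverse event with a partial start date treatment-emergent even when the known part of that date is before dosing, which contradicts the TEAE definition in SAP 13.1

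*SAP*

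**What the plan says.** SAP 6.4 opens with the general statement "No management of incomplete dates will be performed" and says that incomplete dates are labelled as such in the listings. It then gives one allocation rule, triggered as follows: "If the start date of a medication or an adverse event is missing or incomplete and the end date is missing, on or after" dosing. A medication that meets this trigger counts as concomitant and an adverse event as treatment-emergent. The punctuation makes sense only if the end-date condition is met by an end date that is missing, or one that falls on or after dosing.

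SAP 13.1 defines a treatment-emergent adverse event (TEAE) as "an adverse event that occurs after IMP dosing or that was present prior to dosing but was exacerbated between dosing" and study end. Protocol Appendix 2 agrees: "A treatment-emergent AE is an AE that occurs after IMP dosing or that was present prior to dosing but becomes exacerbated". Protocol 10.2.10.2 also has each event classed as pre-treatment or treatment-emergent by reference to IMP intake.

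Pre-dose events are in the data: "Adverse events, including pre-treatment events, will be recorded from the time of consent through the end of the study" (SAP 13.1).

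For medications, SAP 8.4 limits its default to cases that cannot be settled: "If the date value does not allow allocation of a medication to the previous or concomitant category", because a start or end date is missing or incomplete. Neither document gives a matching limit for adverse events.

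**The concern.** One sentence serves two kinds of record that need different tests. A medication still being taken at dosing is concomitant whenever it began. An adverse event still present at dosing is not thereby treatment-emergent; by SAP 13.1 it must have worsened. SAP 6.4 applies the medication logic to both.

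Defaulting to treatment-emergent is sensible when onset cannot be placed relative to dosing. The fault is confined to records where the part of the date that is known already places onset before dosing. For those, a programmer cannot satisfy both 6.4 and 13.1.

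Safety and tolerability are the primary objective, and SAP 13.1 tabulates TEAEs by treatment group, intensity and causality. The groups are small, so a single record can visibly move a percentage. The error can fall in any group, placebo included.

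**Working it through.** The plan states no figure to reproduce. The check applies the two rules to the same records and then sizes the effect of one participant.

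**Rules as coded**
- SAP 6.4: TEAE if the start is missing or incomplete and the end is missing or on/after dosing.
- SAP 13.1: TEAE if onset is after dosing, or if onset is before dosing and the event worsened afterwards.

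**Test records.** The dosing date of 10 Feb 2020 is assumed for illustration. No event worsens.

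| Start | End | TEAE under 6.4 | TEAE under 13.1 |
|---|---|---|---|
| Jan 2020, day unknown | missing (ongoing) | yes | no |
| Jan 2020, day unknown | 12 Feb 2020 | yes | no |
| Jan 2020, day unknown | 5 Feb 2020 | no | no |
| Feb 2020, day unknown | missing (ongoing) | yes | cannot be settled from the start date |

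Rows 1 and 2 are the contradiction. Row 3 shows the end-date condition doing useful work. In row 4 the conservative default is appropriate.

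**How often a month-only date would settle the matter.** SAP 3.4 places screening from Day -28 to Day -2. Assume pre-dose onsets are spread evenly over the W days before dosing, and average over all dosing dates in 2019 to 2022 (1461 days, 48 months, mean month length 1461/48 = 30.44 days). The share of onsets in a calendar month wholly before the dosing month is [W(W+1)/2] / (W × 30.44).
- W = 28: 406 / 852.25 = 0.476, about 48%.
- W = 14: 105 / 426.1 = 0.246, about 25%.

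These are shares of pre-dose onsets that a month-only date could decide. They are not the frequency of the problem, which also requires a partial date and an end date that is missing or on/after dosing. Events lasting into dosing would tend to start nearer to it, so the lower share is the more relevant of the two.

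**Effect of one participant.** SAP section 4 gives 6 active and 2 placebo per panel. With four panels (SAP 3.2) there are 24 active and 4 × 2 = 8 placebo participants, pooled under SAP 6.2. Incidence is the number of participants with at least one TEAE divided by n, so one extra participant adds 1/n:
- dose group: 1/6 = 16.7 points
- pooled placebo: 1/8 = 12.5 points
- all participants: 1/32 = 3.1 points

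This holds only if the participant has no other TEAE. Otherwise incidence is unchanged and only the event count rises by one. If there are 10 or fewer adverse events, SAP 13.1 produces only a listing, and the effect is on the classification shown there.

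**The case against.** The strongest reply is that 6.4 is a deliberate, pre-specified conservative convention and that the affected records will hardly occur. Protocol 9.6.1 asks for date and time of onset. Protocol Appendix 1 provides for consistency checks and queries, and protocol 10.1.3 for a blind review before lock. An illness lasting into dosing would often exclude the participant (inclusion criterion 3, exclusion criterion 12) or be noticed at the D-1 examination. All of this supports calling the problem rare. It does not remove it: events are collected from consent, participants are at home until the evening of D-1, and a mild event need not exclude anyone.

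Conservatism justifies the default where onset is uncertain, but not where the recorded date already shows onset before dosing. In placebo the extra count is not cautious either, because it raises the comparator.

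A reader might go further and infer that the rule could make the drug look harmful or distort dose decisions. The documents do not support that:
- TEAEs are also tabulated by causality, and the causality scale in protocol Appendix 2 assigns an event with an implausible time sequence to the unrelated category.
- Incomplete dates are labelled in the listings, so an affected record can be seen.
- The stopping rules in protocol 7.5 do not use the SAP's treatment-emergent flag.
- The primary endpoint is a broad set of safety parameters analysed descriptively, of which TEAE incidence is only one part.

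**Conclusion.** The contradiction is real and narrow. SAP 6.4 yields a TEAE where SAP 13.1 and protocol Appendix 2 do not, for a non-worsened event whose known start month or year is wholly before dosing and whose end is missing or on/after dosing. This is a stated rule with a wrong result, not a missing detail, because nothing elsewhere limits it for adverse events.

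The importance is small. The number of such records is not given; at zero nothing changes. The 16.7 and 12.5 points are the most that one participant can add to a dose group or to pooled placebo, and they assume that participant has no other TEAE. The causality tables and labelled listings partly offset the effect.

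It would be wrong to infer that the default itself should go. For a fully missing start, or a known part compatible with onset after dosing, 6.4 is a reasonable choice and should stay.

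**What to change.** Keep the SAP 6.4 rule as it stands, including its end-date condition, and add for adverse events: *except where the known parts of the start date show onset before study drug administration, in which case the event is treatment-emergent only if it worsened after dosing*. Leave the medication rule unchanged.

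The end-date condition must be retained. Without it, an event with start February, day unknown, and end 5 February, for dosing on 10 February, would no longer be kept out, although it plainly ended before dosing.

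In the test records, rows 1 and 2 become pre-treatment; rows 3 and 4 do not change. Genuine worsening should not be lost: the severity section of protocol Appendix 2 asks for a separate entry with its own onset date when intensity changes.

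The cost is one sentence and minor programming, and a slightly less conservative rule for events already shown to precede dosing. The labelled listings let the sponsor check quickly whether any record is affected.
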